PROPOSAL SUMMARY

Host Organization: University Hospital Río Hortega

Project Title: Predicting overall survival in glioblastomas using radiomic features of intraoperative ultrasound. A proposal for the creation of an international database of brain tumor ultrasound images.

Type of study: Ambispective observational

Start date & Duration: 1/10/2021 – 30/03/2022

1. Lay Abstract

Predicting the survival of patients diagnosed with glioblastoma (GBM) is essential to guide surgical strategy and subsequent adjuvant therapies. Intraoperative ultrasound (ioUS) is a low-cost, versatile technique available in most neurosurgical departments. The images from ioUS contain biological information possibly correlated to the tumor's behavior, aggressiveness, and oncological outcomes. Today's advanced image processing techniques require a large amount of data. Therefore, we propose creating an international database aimed to share intraoperative ultrasound images of brain tumors. The acquired data must be processed to extract radiomic or texture characteristics from ioUS images. The rationale is that ultrasound images contain much more information than the human eye can process. Our main objective is to find a relationship between these imaging characteristics and overall survival (OS) in GBM. The predictive models elaborated from this imaging technique will complement those already based on other sources such as magnetic resonance imaging (MRI), genetic and molecular analysis, etc. Predicting survival using an intraoperative imaging technique affordable for most hospitals would greatly benefit the patients' management.

2. Scientific Summary

We plan to carry out a multicentre retrospective study of patients operated with GBM diagnosis between January 2018 and January 2020, in order to set the base for future prospective collection of patients. All cases with an ioUS study will be included. All patients must count with B-mode modality. After an pseudonymization process, the images will be uploaded to a private cloud server. Demographic, clinical, conventional radiological, and molecular variables (IDH, MGMT) will also be collected. OS will be defined as the time elapsed between the histopathological diagnosis and the patient's death. The acquired data must be processed to

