3.2 Hypotheses

Intraoperative ultrasound images in B-mode harbour tumor texture features correlated with overall survival in glioblastomas.

3.4 Objectives:

- To determine the relationship between the radiomic features of intraoperative ultrasound B-mode and overall survival in glioblastomas.
- Develop a predictive survival model using the texture features with the highest discriminatory power.
- Validate the model against an external dataset and compare it with currently available predictive models.
- Build a data set that allows exploring various image harmonization techniques that allow the reproducibility of our predictions.
- Establish an international cooperation network (**BraTioUS-DB**) whose objective will be to interchange ultrasound images and clinical data of patients operated on for a brain tumor prospectively from its creation and start-up.

4. Research Plan:

4.1 Study sample:

The cases that meet the inclusion criteria mentioned in the following section will be collected retrospectively to carry out the project's first phase. From January 2018 to January 2020, it is

estimated that each center can contribute with a minimum of 20 cases. Therefore, the total sample size for this phase of the study will be approximately 120 patients.

4.2 Selection of patients:

The inclusion criteria will be:

- Adult patients operated between January 2018 and January 2020 with a pathological diagnosis of WHO grade IV astrocytoma (Glioblastoma).
- Intraoperative ultrasound study that includes B-mode images

The exclusion criteria will be:

- Other histopathological diagnoses. Even though the international database will be established in such a way that other tumor types can be included prospectively.
- Artifacts in ultrasound images that make their analysis impossible
- Stereotactic biopsies.

4.3 Data collection (retrospective phase):

Each center will collect the details of the intraoperative acquisition technique of the ultrasound images. These data should include:

- Manufacturer of the ultrasound equipment,
- Type of probe: linear, curve.
- Footprint size
- Frequency range
- Modality. Essential B-mode, other modes optional.
- Acquisition before or after dural opening.
- Co-registered magnetic resonance images when possible (navigated ultrasound).
- Number of explorers who perform the ultrasound study.

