Of all the B-mode ultrasound images made by each patient, at least three slices will be selected in which the largest tumor diameter is appreciated, the peritumoral region, and healthy parenchyma, ideally in two planes perpendicular to each other.

After pseudonymizing the images, they will be uploaded from each center to a private cloud server with authentication to ensure data privacy. The computing platform will be Box (www.box.com), a leading company in storing and protecting data worldwide. The contents uploaded to the cloud will be protected with integrated controls, specific permissions and robust user authentication systems. Furthermore, each file will be encrypted with AES 256-bit encryption in various locations (FIPS 140-2 certified). The platform also complies with

regulations such as the General Data Protection Regulation (RGPD), the Law of Transfer and Liability of Health Insurance (HIPAA), the Federal Program for Risk Management and Authorizations (FedRAMP). Regarding security, Box Shield (a Box feature) works as a first-level security tool, highlighting, for example, the automatic detection of malware and the prevention of cyberattacks. The details of its characteristics can be consulted at: <https://www.box.com/es-419/shield>.

Along with the images, the demographic and clinical data of each patient will be recorded:

- Karnofsky Functional Rating Scale (KPS).
- Age
- Sex
- Adjuvant treatment received: chemotherapy/radiotherapy
- Percentage of resection of the enhancing tumor volume and non-enhancing peritumoral region. Based on this percentage, resections will be classified as: 100% complete resection (GTR); Subtotal resection > 90% (SBT) and Partial Resection <90% (PR).
- Immunohistochemical data included in the current WHO classification for pathological diagnoses of glial tumors. IDH, ATRX and MGMT mutation.

4.4 Data collection (prospective phase):

Once the international collaborative network has been consolidated and the online platforms have been enabled, glioblastomas and other tumor strains will begin to be collected prospectively.

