4.6 Segmentation

The segmentation process will be performed semi-automatically by an expert neurosurgeon and by a senior neuroradiologist. Segmentation of the area corresponding to the tumor will be performed, avoiding regions cystic/necrotic. The peritumoral area with evidently altered echogenicity will also be segmented. The Dice similarity coefficient will be used to assess the variability between the segmentations made by both examiners.

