The transfer of data about human beings to the repository will only be considered when: informed consents, ethical approval and, where applicable, approval of local data protection authorities cover the purpose for which the data is intended to be used. Since this study involves patients diagnosed with glioblastomas, the cases have perished at the time of data collection. Therefore, the exemption of informed consent will be requested for the retrospective phase of the study (see Annex). On the contrary, for the prospective collection of cases, the informed consent model will be used (see Annex). All data to be transferred to the repository will be pseudonymized. The data owner/data provider will be responsible for the pseudonymization process and ensure that identifiable variables are not transferred to the repository.

7. Communication Plan for Dissemination:

This project's results will be disseminated through its publication in scientific journals and international conferences focused on neuroimaging, ultrasound, neurosurgery, and neuro-oncology.

8. Outputs: Impact, potential beneficiaries and added value:

The research work, aligned with one of the items of the Horizon 2020 program (Health, Demographic Change and Wellbeing) in addition to two of the United Nations Sustainable Development Goals (Health and well-being, 3; Industry, Innovation and Infrastructure, 9), has a great potential for impact, both at a scientific-technical level and a socio-economic level.

Concerning the scientific-technical, it is considered that the development of models for pre-processing, advanced analysis of ultrasound images that apply to commercial scanners and that, in turn, derive in descriptors that generate a large amount of useful information about the macro and microstructural properties of brain tumors, will lead to an increase in the use of advanced ultrasound techniques in clinical practice and will generate an increase in scientific research projects focused on these imaging technique. Furthermore, such models' implementation will substantially improve radiological care (diagnosis, early detection and treatment).

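### Slice choice, artifact exclusion and segmentation in the retrospective phase are not masked to survival, which can already be known, and most of the planned checks would not reveal a resulting bias

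*Protocol*

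**What the plan says.** Section 4.2 includes "Adult patients operated between January 2018 and January 2020". The summary gives the study period as "1/10/2021 – 30/03/2022". To justify a consent waiver, section 6 states that "the cases have perished at the time of data collection".

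Three steps that involve judgement come before feature extraction:

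- **Slices (4.3).** From all of a patient's B-mode images, "at least three slices will be selected in which the largest tumor diameter is appreciated", with the peritumoral region and healthy parenchyma also visible, "ideally in two planes perpendicular to each other". There is no upper limit and no tie-break, and the person who selects is not named.
- **Artifacts (4.2).** One exclusion criterion is "Artifacts in ultrasound images that make their analysis impossible". No assessor or log is given.
- **Segmentation (4.6).** "The segmentation process will be performed semi-automatically by an expert neurosurgeon and by a senior neuroradiologist". Cystic and necrotic regions are left out, and peritumoral tissue with visibly changed echogenicity is included. Agreement between the two readers is measured with the Dice coefficient.

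Section 4.3 also says "Along with the images, the demographic and clinical data of each patient will be recorded": performance status, age, sex, adjuvant treatment, extent of resection, and IDH, ATRX and MGMT. OS and date of death are not in that list. Section 4.8 offers five- and ten-fold cross-validation, a random split, and one collaborating centre as external cohort. Images are pseudonymized, but no section masks anyone to survival or to clinical data.

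**The concern.** The first two objectives are to relate B-mode features to OS and to build a survival model from them. Both need the features to be measured independently of the outcome. If whoever picks frames, rejects cases or draws contours knows how long a patient lived, a slight and unconscious preference for worse-looking images in short survivors is enough to link a feature to OS when no link exists.

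Pseudonymization protects privacy; it does not hide the outcome from a centre handling its own patients. Pre-processing and harmonization act on the chosen frames and cannot undo the way they were chosen. Masking is study conduct that must be settled before collection starts, so an analysis plan written later could not restore it.

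**Working it through.** **1. Can survival be known when images are handled?** The last eligible operation is in January 2020 and the study starts on 1 October 2021. From the end of January 2020 to that date is 11 + 9 = 20 months, against a survival of about 15 months quoted in section 3.1. Together with the statement in section 6, survival times can be available to the treating centres. The protocol does not show that the two segmenters have them.

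**2. Sample size.** Five listed collaborators plus the host, at a minimum of 20 cases each, gives 6 × 20 = 120. This reproduces the stated figure and is used below.

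**3. How large could the effect be?** Everything here except n = 120 is an assumption. A feature has no relation to OS; each patient has 10 candidate frames, of which 3 are used; the between-frame intraclass correlation (ICC) is 0.5 to 0.7. Frames are drawn with weight exp(b·z), where z is the feature in SD units. The sign of b is positive in below-median survivors and negative in the rest. A univariate Cox score test is made at two-sided 5%. With b = 0.25 the preference is exp(0.25) = 1.28 per SD; with b = 0.5 it is exp(0.5) = 1.65. Because the sign flips between groups, the between-group contrast at b = 0.25 is exp(0.25)/exp(−0.25) = 1.65.

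| Preference per SD | SD = total frame SD | SD = within-patient SD | Overall, about |
|---|---|---|---|
| none | 5% to 6% | 5% to 6% | 5% to 6% |
| 1.28-fold | 8% to 15% | 14% to 26% | 9% to 24% |
| 1.65-fold | 16% to 45% | 43% to 70% | 19% to 69% |

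Repeat simulations differ by a point or two, so the last column is a rounded summary. If visual impression correlates only 0.3 to 0.5 with the feature, the 1.28-fold rate is about 5% to 11%.

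**4. Would the planned validation show it?** A second simulation uses 6 centres × 20 patients, exponential OS with median 15 months, 20 features unrelated to OS, 3 of 12 slices, and the top 3 features selected within the training data (300 runs per scenario). The between-slice SD is 0.5 or 1.0 times the between-patient SD, that is, ICC 1/(1 + 0.25) = 0.8 or 1/(1 + 1) = 0.5. In a fraction f of patients the three most extreme slices in the direction of the outcome are taken on one feature. This is a strong lean, chosen to test detection rather than to estimate size.

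| Scenario | C-index, 5-fold CV | C-index, held-out centre |
|---|---|---|
| Masked selection | 0.50 | 0.50 |
| All centres lean, f = 0.25 | 0.51 to 0.52 | 0.51 to 0.53 |
| All centres lean, f = 0.5 | 0.53 to 0.59 | 0.54 to 0.59 |
| All centres lean, f = 1 | 0.62 to 0.70 | 0.62 to 0.70 |
| Only the five development centres lean | 0.50 to 0.67 | 0.50 |

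When the lean is shared, cross-validation and the held-out centre agree within about 0.01 and nothing looks wrong. When the held-out centre does not share it, its C-index stays at 0.50 and exposes the problem.

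**5. Dice.** It measures agreement between two readers. Two unmasked readers can agree closely and lean the same way.

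**The case against.** A reader might infer four stronger things that the protocol does not support.

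- **That no validation could reveal the bias.** Section 4.8 lists a collaborating centre as external cohort, and a centre without the lean would reveal it.
- **That the outcome travels with the images.** The list in section 4.3 holds prognostic variables, not OS, and does not say that selectors or segmenters see them.
- **That the treating centre selects the slices.** The order of the text in 4.3 suggests this, but the sentence is passive and names nobody.
- **That everyone handling images knows the outcome.** The statement in section 6 is a consent argument. If all patients have died, vital status separates no one; the bias needs knowledge of how long each patient lived. That is plausible for treating centres and not shown for the segmenters.

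Other points limit the concern. The largest-diameter rule, the high bar for artifacts and semi-automatic segmentation all restrict discretion. The artifact item excludes cases; it does not invite centres to discard single frames. The illustration ties frame choice to the feature itself, although section 1 says the images hold more than the eye can process, and a univariate test is not the planned analysis. An imaging manual, not at hand, might cover some of this.

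These points narrow the claim and its size. They do not supply masking. An open slice count, a plane rule that is only a preference, and an undefined artifact threshold still leave room for judgement.

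**Conclusion.** The concern holds in limited form. Three judgement steps precede feature extraction, survival times can be known at least to the treating centres, and no section masks those steps to survival or to the clinical data. Cross-validation, a random split and Dice cannot detect outcome-aware handling. A held-out centre detects it only if its own images, and their segmentation, are free of the same lean.

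The protocol makes no false statement here and gives no evidence that bias has occurred. Its size is not derivable from the document. The rise from 5% to roughly 9% to 24% rests on the assumed 1.28-fold preference in every patient, 3 of 10 frames, an ICC of 0.5 to 0.7 and the choice of SD scale; it shrinks towards 5% if the eye sees the feature poorly. It shows that a moderate lean could matter, not that this study has one.

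**What to change.** Amend sections 4.2, 4.3 and 4.6 as follows:

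- **4.3, slices.** Set a fixed number per patient and a fixed selection rule with a tie-break, and state who selects. If centres select, the fixed rule is the main protection, because a centre cannot be fully masked to its own patients.
- **4.3, data.** Keep survival and clinical data in a separate restricted folder, using the access permissions that the section already describes for the cloud platform.
- **4.2, artifacts.** Log every artifact exclusion with its reason, decided without reference to survival.
- **4.6, segmentation.** The two planned readers segment without access to the restricted folder.
- **Lock.** Slices, exclusions and both segmentations are locked before OS is linked.
- **Sensitivity analysis.** Repeat the model without cases from the segmenting neurosurgeon's own centre, since those patients may be recalled.

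The cost is some reordering of work and slightly later linkage, with no extra patients. Central slice selection from all B-mode frames would mask better but is optional: it adds reader work, and upload work for centres that carry the collection themselves (section 9).

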4.5 Pre-processing of images and estimation of radiomic markers

The acquired data must be processed to obtain a series of radiomic markers to perform the study. A pre-processing or harmonization stage will be necessary (cropping, noise cleaning, speckling removal, histogram/intensity normalization) to calculate radiomics measurements.

4.6 Segmentation

The segmentation process will be performed semi-automatically by an expert neurosurgeon and by a senior neuroradiologist. Segmentation of the area corresponding to the tumor will be performed, avoiding regions cystic/necrotic. The peritumoral area with evidently altered echogenicity will also be segmented. The Dice similarity coefficient will be used to assess the variability between the segmentations made by both examiners.

4.7 Radiomic Feature Extraction

In a previous step, the images will be pre-processed by resampling at 1 x 1 mm size. Intensity discretization will also carry out using 256 gray levels and a relative rescaling of intensities using the three-sigma method (± 3 standard deviations [SD]). The next step will be to extract the segmented regions' radiomic features using open-source software Pyradiomics / LifEx.

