obtain a series of radiomic markers to perform the study. A pre-processing stage will be necessary (noise cleaning, despeckling, intensity normalization, filtering) to calculate radiomics measurements (histogram, volumetric, shape, texture, etc.). In the previous stage, a very high number of radiological features per subject will be calculated. Because the number of features is much higher than the data set, to avoid the curse of dimensionality, it will be necessary to reduce their number using feature selection and extraction techniques (standard in pattern recognition and radiomics) that allow choosing those characteristics (or transformations of them) that have greater discriminating power. A predictive model of survival will then be elaborated based on the features selected.

3. Project Details

3.1 Background and Scientific Rationale:

GBM are the most common primary brain neoplasm. The survival of these patients is approximately 15 months despite continuous efforts to find more effective treatments. ioUS is a low-cost, versatile imaging technique available in most neurosurgical departments. These images contain biological information with potential application in surgical practice in addition to being a handy technique for image-guided brain tumor surgery. Advanced modalities, such as contrast-enhanced ultrasound (CEUS), intraoperative ultrasound elastography (IOUS-E), and navigated three-dimensional (3D) ultrasound, currently make it possible to exploit the full potential of this imaging technique to achieve maximal safe tumor resections.

On the other hand, advanced medical image analysis allows the development of predictive survival models using radiomic features. Even though ioUS image quality and resolution could be considered inferior compared to other imaging techniques, such as MRI, there is growing evidence that the ultrasound images contain biological information that can be set as a base to create models that allow classification tasks such as benignity versus malignancy. The ultrasound's capacity as a prognostic marker in response to adjuvant treatments in breast pathology has recently been evaluated. One possible explanation may lie in the fact that echogenicity in the B-mode could be associated with cellularity, which, on the other hand, is related to tumor aggressiveness.

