4.8 Data analysis

Because the number of features is much higher than the data set, it will be necessary to reduce their number using feature selection and extraction techniques that allow choosing those characteristics that have greater discriminating power.

A predictive model of survival will then be elaborated based on the selected features. The performance evaluation strategy of the predictive survival model will be adjusted to the sample size. The options to be tested will be five and ten-fold cross-validation, the random split of the sample into a training cohort and testing cohort (unseen data), and an external validation cohort formed by one of the collaborating centers.

5. Team and Scientific Potential:

The research group that we have assembled has already collaborated in the past and has carried out various tasks focused on integrating non-invasive diagnostic tools for neurological pathologies and creating new imaging methods applicable to neurosurgical patients.

The principal investigator ([name]) is currently collaborating with an international network dedicated to the study and advanced analysis of images in glioblastomas, ReSPOND (Radiomics Signatures for PrecisiON Diagnostics) consortium on glioblastoma (GBM).

At the national level, [name] collaborates with the recently established National Brain Metastasis Network (RENACER), a project promoted by the National Center for Oncological Research. Our center has also collaborated for several years with the National Registry of Central Nervous System Tumors (RETSINE) of the Spanish Research Group in Neuro-Oncology.

Since 2019, the IP is the Coordinator of the Central Nervous System Tumors Committee of the Río Hortega University Hospital.

Our team has collaborated with the Image Processing Laboratory (IPL) of the Higher Technical School of Telecommunications Engineering (HTST) of the University of Valladolid (www.lpi.tel.uva.es), which has been studying diagnostic image processing for years, performing multiple projects and having high-level expertise in this field.

The project will have the collaboration of the following international centers:

1. [name] [name] (Fondazione Policlinico A. Gemelli, IRCSS, Rome, Italy)
2. [name] [name] (Tata Memorial Center, Mumbai, India)
3. [name] [name] (Fondazione Istituto Neurologico Carlo Besta, Milano, Italy)
4. [name] (Philipps University of Marburg, Marburg, Germany)
5. [name] (CHRU de Tours and Inserm U1253, Tours, France).

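### With 256 grey levels on a 1 mm grid, entropy-type texture features can track region size, so section 4.8 should require a selected texture feature to add to area before it is called texture

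*Protocol*

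**What the plan says.** Section 4.7 of the protocol sets the grid and the number of grey levels: "the images will be pre-processed by resampling at 1 x 1 mm size. Intensity discretization will also carry out using 256 gray levels". It adds "a relative rescaling of intensities using the three-sigma method", at plus or minus 3 SD, without saying whether the SD is that of the image or of the segmented region. Extraction follows: "The next step will be to extract the segmented regions" (their radiomic features, with one of two named packages). Section 4.5 places "cropping, noise cleaning, speckling removal, histogram/intensity normalization" before this, at unstated strength.

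Section 4.3 selects 2D slices, at least three per patient. Section 4.6 leaves cystic and necrotic parts out of the tumour region. Section 2 plans "to calculate radiomics measurements (histogram, volumetric, shape, texture, etc" and so on, which makes size measures candidates beside texture. Section 4.8 reduces the features by "techniques that allow choosing those characteristics that have greater discriminating power". The hypothesis in section 3.2 is specifically about texture: "Intraoperative ultrasound images in B-mode harbour tumor texture features correlated with overall survival in glioblastomas".

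**The concern.** A co-occurrence matrix counts how often each pair of grey levels occurs in neighbouring pixels. With 256 levels it has far more cells than a small 2D region on a 1 mm grid has pixel pairs. Most cells are then empty. Joint entropy is limited by the number of counts, and that number grows with area. Energy and the information-correlation measures are exposed in the same way.

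The concern is about interpretation. If solid-region area is related to overall survival, selection by discriminating power could pick such a feature because it carries size, and the study would report size as texture. None of the validation options in section 4.8 (cross-validation, random split, external centre) would show this, because size would predict in the held-out patients too.

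**Working it through.** **Inputs from the protocol.** 1 mm pixels, 256 levels, plus or minus 3 SD (4.7); 2D slices (4.3); about 120 patients (4.1), which agrees with the host and five listed centres at 20 cases each: 6 × 20 = 120. Section 6 says that the retrospective patients have died, so the simulations use 120 deaths without censoring. The protocol gives no figure for region size or matrix occupancy.

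**Assumed.** Co-occurrence features are extracted at distance 1 in four directions; regions are discs 20 to 50 mm across; texture is smoothed Gaussian noise. Fine texture means smoothing of 0.5 to 1.5 px, and smooth texture 1 to 6 px. For whole-image rescaling, tumour SD is 0.3 to 1.0 or 0.1 to 0.4 of background SD.

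**Step 1: sparsity.** Unique cells of a symmetric matrix = L(L+1)/2. For L = 256 this is 256 × 257/2 = 32,896; for 64 it is 2,080; for 32 it is 528.

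| Diameter (mm) | Pixels | Pairs, 4 directions | Pairs per cell, 256 | 64 | 32 |
|---|---|---|---|---|---|
| 20 | 316 | 1,166 | 0.035 | 0.56 | 2.2 |
| 30 | 716 | 2,718 | 0.083 | 1.31 | 5.1 |
| 40 | 1,264 | 4,862 | 0.148 | 2.34 | 9.2 |
| 50 | 1,976 | 7,662 | 0.233 | 3.68 | 14.5 |

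**Step 2: why entropy follows area.** Joint entropy cannot exceed log2(number of counts). In one direction the symmetric counts are about 2 × (πd²/4 − d): 323 at d = 15 mm and 5,535 at 60 mm. The cap therefore rises from log2(323) = 8.3 to log2(5,535) = 12.4 bits through area alone.

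**Step 3: strength of the link.** Spearman correlation of joint entropy with diameter at 256 levels, 120 regions, mean of 6 runs, directions merged / averaged:

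| Rescaling | Texture | One slice | Three slices pooled |
|---|---|---|---|
| Whole image, SD 0.1-0.4 | smooth | 0.12 / 0.22 | 0.08 / 0.12 |
| Whole image, SD 0.1-0.4 | fine | 0.20 / 0.42 | 0.11 / 0.23 |
| Whole image, SD 0.3-1.0 | smooth | 0.36 / 0.61 | 0.19 / 0.41 |
| Whole image, SD 0.3-1.0 | fine | 0.67 / 0.92 | 0.34 / 0.69 |
| Per region | smooth | 0.78 / 0.95 | 0.47 / 0.87 |
| Per region | fine | 0.98 / 1.00 | 0.93 / 0.99 |

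At 32 levels the one-slice values fall to 0.23 / 0.48 (per region, fine) and to at most 0.15 / 0.16 (whole image, variable spread), so the stated number of levels drives most of the effect. Contrast, correlation and inverse difference moment stay at or below 0.05 (fine) and 0.17 (smooth), almost the same at 32, 64 and 256 levels.

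A second simulation with diameters of 15 to 55 mm and other smoothing and spread assumptions gave R² of entropy on log area from about 0.01 (whole image, directions and three slices pooled) to about 1.00 (per region).

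**Step 4: consequence when area competes.** Exponential survival, no true texture effect, one slice, directions merged, Cox Wald tests, area hazard ratio (HR) of 1.2 / 1.3 / 1.5 per SD (assumed), 10 cohorts × 150 draws. Share of draws in which entropy is significant and also stronger than area:

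| Setting | Hazard linear in area | Hazard follows log area |
|---|---|---|
| Per region, fine | 14 / 19 / 12% | 24 / 33 / 37% |
| Whole image, SD 0.3-1.0, fine | 9 / 8 / 3% | 10 / 10 / 5% |
| Whole image, SD 0.1-0.4, smooth | 3 / 2 / 0% | 4 / 2 / 0% |

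The reference is 3 to 6% with no area effect (HR 1.0; separate run, 8 cohorts × 100 draws). Averaging directions raises whole-image, SD 0.3-1.0, fine to 15 / 15 / 11% (area) and 21 / 28 / 24% (log area).

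**Step 5: effect of adjustment.** With log area in the model, entropy is significant in 4 to 7% in every setting. With linear area only, the range is 4 to 15%; the 14 to 15% occurs with per-region rescaling, fine texture, HR 1.5 and a log-area hazard.

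**The case against.** The strongest reply is that 256 levels and 1 mm do not produce harm alone. The size of the effect turns on rescaling scope, direction merging, slice pooling and filter strength, which a protocol may leave to an SAP or imaging manual. That stands: their absence is not the point here. The two settings that make the matrix sparse are, however, fixed in section 4.7.

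The milder reading also fits the text better. Section 4.7 processes the images first and extracts from the regions afterwards, which leans towards whole-image rescaling, and despeckling is planned. Under that reading with merged directions and hazard linear in area, the rates of 3 to 9% and 0 to 3% are close to or below the 3 to 6% reference. This stands too, and it limits the weight of the point.

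The consequence was simulated for one slice only, although at least three are planned; pooled slices weaken the link. It also rests on an assumed relation between area and survival, and solid-region area is not whole-tumour size.

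Size measures are already candidates. That reduces the risk but does not remove it, since selection may still prefer entropy to area.

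A reader might infer that at 256 levels the texture features are merely size, so that the section 3.2 hypothesis cannot be tested. The documents do not support this. They give no region sizes, no feature list and no filter strength, and several co-occurrence features are little affected. Nor is the aim of predicting survival undermined, because a feature that carries size may still predict.

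**Conclusion.** The point holds as a limited one, for consideration rather than as an error that must be corrected. If co-occurrence features are used on 2D regions of roughly 20 to 50 mm, the matrix is sparse by arithmetic, and joint entropy can track area. The strength cannot be fixed from the protocol: the one-slice correlation is about 0.1 to 0.9 under whole-image rescaling and about 0.8 to 1.0 under per-region rescaling. Whole-image rescaling with equal tumour spread in all patients would give up to 1.00, but that is an idealised case.

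Mislabelling size as texture further requires that area be related to survival. Its excess over chance is clear for per-region rescaling with fine texture. For whole-image rescaling with merged directions it is small or absent, and larger if directions are averaged. The rates compare one entropy feature with area; they do not describe selection from a full feature set. Confidence is medium, because every region, texture and hazard input is assumed.

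**What to change.** **Main change, in section 4.8.** Report the correlation of each selected texture feature with region area, and describe the feature as a texture predictor of overall survival only if it adds to a model that already contains area. Enter area as log area or as a flexible term, since linear area alone did not always remove the false signal. The size measures are already planned, so the cost is a little more analysis and possibly fewer features labelled as texture.

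**Alongside, in section 4.7.** One sentence stating whether the three-sigma rescaling uses the image or the region.

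**Optional sensitivity analysis, not a replacement for 256 levels.** Repeat the matrix-based features at 32 or 64 levels, and report whether the selected features and their correlation with area change. This costs one further extraction. It reduces the size dependence without removing it: per region, fine, one slice, 0.23 / 0.48 remains at 32 levels and 0.54 / 0.86 at 64. Coarser levels also lose intensity resolution (with whole-image rescaling and fine texture, a median of 21, 13 or 9 of 32 levels is occupied as the assumed tumour spread falls) and comparability with 256-level extractions.
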